8.4.2 Secondary Efficacy Endpoints

The secondary endpoints are:

- The incidence of adverse events (AEs), incidence of serious AEs (SAEs), incidence of study treatment related AEs, and the incidence of investigational device related AEs

Secondary endpoint data from this observational study will be summarised descriptively. Continuous parameters may include mean, standard deviation, median, minimum, and maximum.

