10.0 Direct Access to Source Data / Documentation

Data will be collected on paper case report forms (CRFs) by appropriately trained delegated members of the patient's healthcare team at the clinical site. Only designated members of the team will be allowed to record and / or correct data in the CRFs. CRFs

will be provided by the Sponsor to the site for completion together with CRF completion guidelines. All CRFs for the study, can be found in Appendix 3 of this protocol. Patients will be assigned a unique study identification number (participant number and initials) and will be identified only by this unique identifier on CRFs and on source documents by name and date of birth. No personal identifier will be used in any publication or communication used to support this research study. The participant identification number will be used if it becomes necessary to identify data specific to a single participant. The monitors, auditors, personnel authorised by the Sponsor, the local IRB, and regulatory agencies are eligible to review medical and research records related to this study as a part of their responsibility to protect human participants in clinical research and will be given direct access to source data and documentation (e.g., medical charts/records, printouts etc.) for source data verification, provided that participant confidentiality is maintained in accordance with local requirements. Access to electronic medical records may be governed by institution policy and each site will be required to ensure access while remaining compliant with institutional requirements.

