-------------------------------	-------------------------------	-------------------------------	-------------------------------	-------------------------------	-------------------------------	-------------------------------	-------------------------------	-------------------------------	--------------------------------	--------------------------------

CASE REPORT FORM	BASELINE (DAY 0)			DATE (DD/MM/YYYY)				
STUDY SITE:	THE ROYAL STOKE UNIVERSITY HOSPITAL							
PRINCIPAL INVESTIGATOR:	[name]							
SITE NUMBER	0	2	5	PATIENT NUMBER	0		PATIENT INITIALS	

Has the patient experienced any Adverse Events since signing the Informed Consent?

Yes No

If yes, please comment below:

CRF completed by:

Print Name: _____ Signature: _____ Date: ____/____/_____

To be completed by Principal Investigator:

I am confident that the information supplied in this case record form is complete and accurate data.

Signature: _____ Date: ____/____/_____

Follow-up Day 1 (please note days 1-9 CRFs will be the same)

CASE REPORT FORM		FOLLOW-UP 1 (DAY 1)			DATE (DD/MM/YYYY)	
STUDY SITE: PRINCIPAL INVESTIGATOR:		THE ROYAL STOKE UNIVERSITY HOSPITAL [name]				
SITE NUMBER		0  2  5 	PATIENT NUMBER	0   	PATIENT INITIALS	

How many hours did the patient wear the geko™ device for?					_____ hours
How well did the geko™ device stick to the patient's leg?					
Very Well Remained attached 	Well Detached in small area 	Poorly Detached over large area 	Very Poorly Detached completely 	Not at all Would not stick at all 	

If any level of detachment has been indicated, please provide a comment below:

Did the patient need any additional fixation to keep the geko™ device in position?				
None 	Micropore Tape 	Adhesive Accessory 	OnPulse™ Knee Strap 	

If removed was the geko™ device easily re-applied?				
Yes 	No 	N/A 		

If no, please comment below:

Overall, how comfortable was the geko™ device for the patient to wear?				

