-------------------------------	-------------------------------	-------------------------------	-------------------------------	-------------------------------	-------------------------------	-------------------------------	-------------------------------	-------------------------------	--------------------------------	--------------------------------

Has the patient experienced any Adverse Events since signing the Informed Consent?

Yes No

If yes, please comment below:

CRF completed by:

Print Name: _____ Signature: _____ Date: ____/____/_____

To be completed by Principal Investigator:

I am confident that the information supplied in this case record form is complete and accurate data.

Signature: _____ Date: ____/____/_____

Final Follow-up Day 10

CASE REPORT FORM	FINAL FOLLOW-UP 10 (DAY 10)			DATE (DD/MM/YYYY)	_____/_____/_____					
STUDY SITE: PRINCIPAL INVESTIGATOR:	THE ROYAL STOKE UNIVERSITY HOSPITAL [name]									
SITE NUMBER	0	2	5	PATIENT NUMBER	0			PATIENT INITIALS		

How many hours did the patient wear the geko™ device for?					_____ hours
How well did the geko™ device stick to the patient's leg?					
Very Well Remained attached 	Well Detached in small area 	Poorly Detached over large area 	Very Poorly Detached completely 	Not at all Would not stick at all 	

If any level of detachment has been indicated, please provide a comment below:

Did the patient need any additional fixation to keep the geko™ device in position?				
None 	Micropore Tape 	Adhesive Accessory 	OnPulse™ Knee Strap 	

If removed was the geko™ device easily re-applied?				
Yes 	No 	N/A 		

If no, please comment below:

Overall, how comfortable was the geko™ device for the patient to wear?				
Very Comfortable 	Comfortable 	Uncomfortable 	Very Uncomfortable 	Extremely Uncomfortable 

If any discomfort has been indicated, please provide a comment below:

Did the patient sleep with the device on?	Yes 	No 
---	------------------------------	-----------------------------

Any other comments – please add below

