Day 10 final assessment and patient participation completed. Please complete Exit CRF

CASE REPORT FORM	FINAL FOLLOW-UP 10 (DAY 10)		DATE (DD/MM/YYYY)	____ / ____ / _____
STUDY SITE: PRINCIPAL INVESTIGATOR:	THE ROYAL STOKE UNIVERSITY HOSPITAL [name]			

SITE NUMBER

0	2	5
---	---	---

 PATIENT NUMBER

0		
---	--	--

 PATIENT INITIALS

--	--

CRF completed by:

Print Name: _____ Signature: _____ Date: ____ / ____ / _____

To be completed by Principal Investigator:

I am confident that the information supplied in this case record form is complete and accurate data.

Signature: _____ Date: ____ / ____ / _____

Exit Day 10

CASE REPORT FORM	EXIT			DATE (DD/MM/YYYY)	____ / ____ / ____					
STUDY SITE:	THE ROYAL STOKE UNIVERSITY HOSPITAL									
PRINCIPAL INVESTIGATOR:	[name]									
SITE NUMBER	0	2	5	PATIENT NUMBER	0			PATIENT INITIALS		
Study Exit Date (DD/MM/YYYY)	____ / ____ / ____									
Date of Last Assessment (DD/MM/YYYY)	____ / ____ / ____									
Last Assessment Completed	Baseline  Follow-up 1  Follow-up 2  Follow-up 3  Follow-up 4  Follow-up 5  Follow-up 6  Follow-up 7  Follow-up 8  Follow-up 9  Follow-up 10 									
Reason for Exit from Study	Study completed  Lost to follow-up  Non-compliance  Medical contraindication  Consent withdrawn  Other** 									
**Additional explanation required:										

CRF completed by:

Print Name: _____ Signature: _____ Date: ____ / ____ / ____

[figure not shown]
To be completed by Principal Investigator:

I am confident that the information supplied in this case record form is complete and accurate data.

[figure not shown]
Signature: _____ Date: ____ / ____ / ____

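### The AE question on the Day 0–9 forms looks back to consent every time, so after a patient's first AE the tick box cannot signal a new, recurrent or different one

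*Combined protocol and SAP*

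**What the plan says.** The secondary endpoints (Sections 2.1.2 and 8.4.2) are all AE incidences: "The incidence of adverse events (AEs), incidence of serious AEs (SAEs), incidence of study treatment related AEs", plus AEs related to the investigational device. Section 8.4.2 plans a descriptive summary. It does not say whether incidence means patients or events, and it gives no counting rule.

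The data come from the forms in Appendix 3. The baseline form asks "Has the patient experienced any Adverse Events since signing the Informed Consent", and the Day 1 form repeats the same words. The Day 1 form stands for the rest of the series: "please note days 1-9 CRFs will be the same". Under the Yes/No tick the only further field is "If yes, please comment below".

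The Day 10 form has no AE item. It closes with "Day 10 final assessment and patient participation completed. Please complete Exit CRF", and the Exit form has no AE item either. Table 1 nevertheless marks AE assessment under Days 1–10, while the list of Day 10 data in Section 4.3 leaves it out.

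No AE log appears, and Section 10.0 states "All CRFs for the study, can be found in Appendix 3 of this protocol".

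**The concern.** The outcome items at the top of each follow-up form (hours worn, adhesion, comfort, sleep) concern the device just worn. The AE item alone runs back to consent. A nurse who answers it literally must tick Yes on every form after a first event, even if that event resolved within a day. From then on the tick carries no information about the latest wear interval. Nothing on the form asks when an event began, whether it is new or continuing, whether it was serious, or whether it was related to treatment or device.

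This matters most for skin reactions. The rationale for the new hydrogel is lower skin irritation (Section 1.3), and the Instructions for Use in Appendix 4 list irritation as a side effect that may come back. A skin reaction that follows an unrelated AE, or a second reaction after a first, is the kind of event the tick cannot show. If it is not written down on the day, it may not be recoverable later.

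**Working it through.** The plan states no AE rate or count, so there is no figure to reproduce. The check has four steps.

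**1. Forms that carry the item.** Day 0 plus Days 1–9 gives 1 + 9 = 10 forms. Day 10 and Exit carry none.

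**2. What the tick shows.** If the first AE is recorded on the Day k form, the literal answer is Yes on 10 − k forms: 10 for k = 0, 9 for k = 1, 2 for k = 8, 1 for k = 9. Only the first of these is informative. Take an unrelated AE on Day 2 and skin irritation on Day 5. The tick is Yes on 10 − 2 = 8 forms, and Day 5 looks the same as Day 4.

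**3. Effect on each summary.**
- *Patients with any AE through Day 9:* correct. Ever since consent is the right window for this quantity.
- *Event counts and recurrences:* cannot be obtained from the tick. They depend on the comment.
- *Patients with a serious, treatment-related or device-related AE:* in the example, the patient enters the device-related incidence only if the Day 5 comment mentions the irritation and its relation to the device, or if the physician reports it under Section 9.1. The missing seriousness and relatedness fields are the larger cause here. The look-back wording adds to it by removing the prompt.

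**4. Illustrative size.** Let h be the chance of a new AE per form. It is an assumption, not from the documents, varied from 0.01 to 0.10. Assume independence, at most one new event per form, all ten forms completed, and 20 patients per phase (Section 3.2).

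- Patients with at least one AE: p = 1 − (1 − h)^10
- Events per phase: 20 × 10 × h = 200h
- Second or later events per phase: 200h − 20p
- Their share of all events: 1 − p/(10h)

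| h | p, either wording | Events per phase | Second or later | Share |
|---|---|---|---|---|
| 0.01 | 9.6% | 2 | 0.1 | 4% |
| 0.02 | 18.3% | 4 | 0.3 | 9% |
| 0.05 | 40.1% | 10 | 2.0 | 20% |
| 0.10 | 65.1% | 20 | 7.0 | 35% |

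The last two columns are events with no signal from the tick. They are lost only if the comment and the other records also miss them. Shorter stays shrink the share. Section 8.2 plans on 4 days of use; with four forms (Days 0–3) the share is 1 − [1 − (1 − h)^4]/(4h). That is 1 − 0.0394/0.04 = 1.5% at h = 0.01 and 1 − 0.3439/0.4 = 14% at h = 0.10.

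**The case against.** The best defence is that the tick is not the only record. Every Day 0–9 form has a comment line where a second event can be written. Section 9.1 requires device-related AEs to reach the sponsor within 24 hours with a full description. It also makes the treating physician responsible for reporting SAEs under local rules. The medical record is the primary source (Section 13.1), and CRFs are verified against it (Section 11.2). Section 10.0 says the forms "will be provided by the Sponsor to the site for completion together with CRF completion guidelines". Those guidelines, and the Data Management Plan named in Section 13.2, are not in the documents and may already restrict the item to new events.

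Much of this stands, and it limits the point to a risk of loss. It does not remove it. The comment has no prompt, the 24-hour route covers device-related events only, and nothing in the documents narrows the printed question.

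A reader might infer more than the documents support:

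- *That the AE incidence endpoints are distorted as a whole.* Read as patients with any AE, the total is right through Day 9.
- *That one event will be counted up to ten times.* With onset spread evenly over Days 0–9 and a full stay, one event gives on average 55/10 = 5.5 Yes forms, but no section plans to count Yes forms as events. The figure describes an analysis nobody has proposed.
- *That second events are necessarily hidden, or cannot be tied to a device.* The comment can hold them. Each patient wears one device type, so attribution to T3 or XT-3 is not in doubt. Forms are dated and lot numbers recorded, so the first Yes places a first event within about a day.
- *That recording habits will drift between the two sequential phases.* Such a drift could not be separated from the device, but the documents give no sign of one. They describe one site and trained recorders.
- *That every daily form asks the question.* Day 10 does not.

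**Conclusion.** The point holds in a limited form. On the Day 0–9 forms the tick stops being informative after a patient's first AE. Recurrences, event counts, and serious or related AEs that come second then depend on free text and on partial outside routes. Under the stated assumptions the events without a tick signal range from 4% to 35% of all events with full follow-up, and from 1.5% to 14% with four forms. The true AE rate is unknown, so these are bounds for illustration and not a forecast. The conclusion assumes that the completion guidelines do not already limit the item to new events. The primary endpoint and the sample size are untouched. The change is worth making because it is small and the information cannot be reliably rebuilt afterwards.

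**What to change.** - On the Day 1–9 forms, ask whether there has been any new or worsened adverse event since the last assessment. Keep the look-back to consent on Day 0 only.
- Put the same item on the Day 10 form, and bring Section 4.3 and Table 1 into line. The Exit form, which early leavers complete, should carry it too.
- Add one line per event: description, onset date, stop date, new or continuing, serious or not, related to study treatment or not, related to the device or not. Rewording alone would still leave three of the four secondary endpoints without structured fields.
- In Section 8.4.2, define incidence as the number and proportion of patients with at least one event of each class. Give event counts as a separate summary, with each event counted once by onset date.
- If the completion guidelines already restrict the item to new events, make the printed question say so.

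The cost is a small CRF edit and slightly more recording for each event. No visits are added.

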Appendix 4: Instructions for Use and Fitting Instructions geko™ X-T3

[figure not shown]
1 Location

[figure not shown]
2 Cleaning

[figure not shown]
3 Fitting

[figure not shown]
4 Turning On

[figure not shown]
5 Settings

Switching Off

7 Removing

The geko™ device is a neuromuscular electro-stimulation medical device and its intended use is:

- to increase blood circulation
- for the prevention of venousthrombosis
- for the prevention and treatment of oedema
- for the treatment of venous insufficiency and ischaemia

The device works by increasing blood circulation by stimulating the common peroneal nerve.

It is to be used on a single patient, in hospital, clinic and home environments. Apply to the affected leg or legs as advised by your Healthcare Professional (e.g. Nurse or Doctor). Patients should be trained in the positioning and operation of the device.

The geko device is intended for up to 24 hours continuous use, until it is no longer needed.

It may be removed for short periods of time when washing or having various tests (see warnings and precautions). Each device is single use and should be replaced every 24 hours, the device has an additional 6 hours run time.

Read this document fully before use and use only as instructed. Improper use of this device can be dangerous. Do not switch on unless correctly attached to the patient.

If assistance is required or to report difficulties, unexpected operation or events, contact the manufacturer. Visit the website for further advice and usage tips.

► Fitting Instructions

1 The marker line ►●◀ on the geko device should line up with the fibula head, a round lump below the knee on the lower leg. Ask your healthcare provider if you need help (e.g. nurse or doctor).

2 It should be applied to clean, dry skin. If there is too much hair in the area it should be removed using trimmers or clippers. Do not shave as this may cause irritation. Wash the skin in the area where the device will be fitted with mild soapy water, rinse, and dry thoroughly; do not apply any moisturizer.

3 Remove the film from the geko device and place the marker line ►●◀ over the fibula head (round lump). Attach the short end round the front of the leg and the longer end towards the back of the leg. The geko device should not be loose, peel off one end and tighten if needed. When correctly fitted, the + button will always be at the front of the leg.

4 To turn on, use a short press of the + button.

5 There are 11 settings, shown by the number of times the light flashes before a pause. Use the + button to increase the setting and - button to decrease.

When working properly geko will cause a visible movement of the muscles in the lower leg, moving the foot out and up, which should continue throughout the whole treatment.

6 To turn it off, hold + button down for 3 seconds. When the button is held the light will flash quickly and when turned off the flashing will stop.

7 Remove carefully in one piece, to avoid damaging the skin.

If stimulation is not achieved geko can also be fitted in alternative positions, see the website for further details.

► Side Effects

Skin Inflammation or Irritation

In some cases, skin inflammation or irritation can develop in the contact area: either remove the device or re-attach in the alternative fitting positions. If the condition persists or recurs, obtain specialist medical advice before resuming use.

► Warnings

Seek specialist medical opinion if the patient is/has:

- Implanted electronic devices (e.g. a cardiac pacemaker).
- Recently diagnosed or suspected DVT.
- Pregnant or breastfeeding.
- Diagnosed heartcondition.
- Epilepsy.
- Had recent surgery where muscle contractions may disrupt the healing process.
- Used the device for 28 consecutive days.

Do not use:

- During any activity in which involuntary muscle contractions may put the user or others at risk of injury (e.g. Driving or operating machinery).
- When bathing or showering – switch off the device and remove temporarily.
- If the device has been worn by another individual – this will carry risk of infection.
- If packaging is open or damaged.
- If device is damaged.

Device should not be used on the following areas of the body:

- Head.
- Eyes.
- Mouth.
- Neck (especially the carotidsinus).
- On the chest, upper back or crossing over the heart. This may increase the risk of cardiac fibrillation.

Do not apply over or near the following:

- Sore, infected or inflamed areas, broken skin or skin eruptions, e.g. phlebitis, thrombophlebitis, varicose veinsetc.
- Cancerouslesions.

Do not use in proximity of the following equipment/environments (which could result in the possible degradation of the performance of geko):

- Short wave/ microwave equipment (i.e. within 1m).
- Portable RF communications equipment (including peripherals such as antenna cables and external antennas) (i.e. within 30cm).
- Heat sources, such as fires or radiant heaters.

Do not use in oxygen rich environments.

Use on children - the safety of the device has not been tested in children; we do not recommend using the device on children.

► Precautions

- Keep out of the reach of children and pets.
- Do not place the geko device in the mouth; it is a choke and potential allergic hazard.
If geko or any component is swallowed seek IMMEDIATE medical assistance. Serious harm could be caused if the battery is swallowed.
- No modification of this equipment is allowed.
- Excessive force may damage the device.
- MRI -The device should be removed before the patient undergoes MRI as it contains ferromagnetic components.
- ECG -The device should be switched off during ECG monitoring using leg electrodes as it may interfere with ECG leg electrode signals.

► Storage and Operation

When storing geko keep it in the protective foil pouch. It can be stored in a temperature range of -25°C to 40°C, but we recommend storing the device up to 30°C.

► Classification

The device is internally powered by a non-replaceable CR2032 lithium ion coin cell battery. The battery is intended for continuous operation.

Type BF applied part – for direct electrical contact to patient but not direct cardiac application. The whole device is the applied part.

► Output Specifications

The device provides square wave, asymmetric, charge balanced stimulation pulses at a rate of 1Hz. The pulses are of a constant current between 27mA and 54mA, and with pulse widths between 35µs and 560µs, according to the stimulation level set. The stimulation intensity increases progressively by increasing the electrical charge in each pulse. There are 11 settings in total. For further information including operating specifications visit the website. The software revision level is identifiable through the Lot number.

► EMC Declaration

Use of the geko device adjacent to other

electrical equipment should be avoided because it could result in improper operation. If such use is necessary, geko and the other electrical equipment should be observed to verify that they are operating normally. The geko device is certified to EN 60601-1-2:2015 regarding Electromagnetic Compatibility.

Medical Electrical Equipment needs special precautions regarding EMC and needs to be put into service according to the EMC information provided on the website. The geko device may switch off if exposed to high levels of electromagnetic disturbance.

► Disposal

